19. RE-USABLE RESPIMAT® SMI PRESCRIPTION

Analysis Set: FAS

Re-usable Respimat® prescription data will be collected under the “Respimat® Exposure” eCRF page. The prescription at study entry of each type of re-usable Respimat® SMI product will be analysed overall and by patient cohort. The following will be described overall and for each type of re-usable Respimat® SMI product prescribed at study entry:

- Duration of use of re-usable Respimat® SMI product during the study period (days) - calculated relative to prescribed date.
- Pack type: Cartridges only, Inhaler and cartridges.
- Pack size: 30 days (1 month), 90 days (3 months).

Document:	\	.net\Enterprise\Sites\USCBG\Depts\BioStat\Boehringer\Documentation\SAP\Final
Author:		Version Number: 1.0

Template No.: RWI_TP_BIOS0013 Revision 1 Reference: RWI_WI_BIOS0015

Effective Date: 15Jun2018

Additionally, at the time of the follow-up assessment, a single question will be asked to all patients to confirm the use of a re-usable version of Respimat® SMI during the study period as follows:

- What type of inhaler have you been using since commencing the study?: Re-usable inhaler, Disposable inhaler.

Derivations:

- Duration of re-usable Respimat® SMI product prescribed at study entry (days) = $[(\text{End of study date} - \text{Prescribed date}) + 1]$.

Details on conversion factors used for dates and on handling of partial dispensed date of reusable Respimat® SMI are described in [Appendix 1](#) and [Appendix 2](#), respectively.

20. OUTCOMES

20.1 Primary Outcome

The primary outcome of the study is the total PASAPQ score with re-usable Respimat® SMI at study end (follow-up assessment, 4-6 weeks after study entry). Total PASAPQ score is a measure of patient's satisfaction regarding the handling of the re-usable Respimat® SMI and will be analysed using the relevant components of the self-administered 15-item PASAPQ (see [Appendix 3](#)).

Document: \\ .net\Enterprise\Sites\USCBG\Depts\BioStat\Boehringer\Documentation\SAP\Final
Author: Version Number: 1.0
Version Date: 100CT2019

Template No.: RWI TP BIOS0013 Revision 1

Reference: RWI WI BIOS0015

Effective Date: 15Jun2018

Derivations:

Total score will be the sum of the 13 items related to performance and convenience PASAPQ domains (7 items for performance domain: Q1-5 and Q10-11 and 6 items for convenience domain: Q6-9 and Q12-13).

Each PASAPQ item has Likert-type response options ranging from 1 to 7 (1 = very dissatisfied, 2 = dissatisfied, 3 = somewhat dissatisfied, 4 = neither dissatisfied nor satisfied, 5 = somewhat satisfied, 6 = satisfied, 7 = very satisfied).

To calculate the total and domain scores, the items within each domain are first summed and then transformed to a 0 (least) to 100 (most) point scale, with higher scores indicating greater satisfaction:

- $Performance\ score = 100 * [(Q1+Q2+Q3+Q4+Q5+Q10+Q11)-7] / (49-7)$.
- $Convenience\ score = 100 * [(Q6+Q7+Q8+Q9+Q12+Q13)-6] / (42-6)$.
- $Total\ score = 100 * [(Q1+Q2+Q3+Q4+Q5+Q6+Q7+Q8+Q9+Q10+Q11+Q12+Q13)-13] / (91-13)$.

20.1.1 Analysis of Primary Outcome

Analysis Set: FAS

The primary objective of this study is to assess patient satisfaction with the re-usable Respimat® SMI measured by the total PASAPO score at study end.

The primary outcome analysis of total PASAPQ score will be performed overall and by patient cohort. All data required for the analysis of the primary outcome will be collected from the “PASAPO (ePRO)” or “PASAPO (Paper)” eCRF pages.

Document: \\net\Enterprise\Sites\USCBG\Depts\BioStat\Boehringer\Documentation\SAP\Final

Author:

Version Number:

10

Version Date:

100CT2019

Template No.: RWI TP BIOS0013 Revision 1

Reference: RWI WI BIOS0015

Effective Date: 15-Jun-2018

Total PASAPQ score will be summarised using descriptive statistics for continuous variables. The mean total PASAPQ score will be presented together with the corresponding 95% CI.

In addition, total PASAPQ score will be categorised as follows: 0 to ≤ 20 , > 20 to ≤ 40 , > 40 to ≤ 60 , > 60 to ≤ 80 , > 80 to ≤ 100 .

20.1.2 Missing Data Methods for Primary Outcome

A patient must answer at least half of the items in the performance and convenience domains in order to calculate a score for that domain. The total score will be calculated only when both domains have computable scores and is calculated as the sum of the 13 items after substitution for missing items at the domain level has taken place.

Missing data in the PASAPQ will be handled as follows [\[5\]](#):

- If half or more than half of the items in the individual domains (performance and convenience) of the PASAPQ are missing for a patient, no score is calculated for that domain, and the PASAPQ domain score is marked as missing.
- If a patient answers at least half of the items in the domain, values for missing items will be imputed using the mean of the remaining, non-missing items in that domain. Total and domain scores will be calculated as described in [Section 20.1](#).

20.2 Secondary Outcomes

The secondary outcomes of the study are as follows:

For all *Respimat® SMI patients*, the following will be described at study end:

Document:	\	.net\Enterprise\Sites\USCBG\Depts\BioStat\Boehringer\Documentation\SAP\Final	
Author:		Version Number:	1.0

Template No.: RWI_TP_BIOS0013 Revision 1

Reference: RWI_WI_BIOS0015

Effective Date: 15Jun2018

- Total performance PASAPQ score (see [Appendix 3](#)).
- Total convenience PASAPQ score (see [Appendix 3](#)).
- Overall satisfaction item score (see [Appendix 3](#)).
- Question on willingness to continue with re-usable Respimat® SMI (see [Appendix 3](#)).
- Questions on ease of handling of re-usable Respimat® SMI (see [Appendix 4](#)).

For *Respimat® SMI*-experienced patients switching from a disposable to a re-usable *Respimat® SMI* at study entry the following will be assessed/described at study end:

- Difference in the mean total PASAPQ score between study entry (baseline visit) and study end (follow-up assessment).
- Question on preference for re-usable or disposable Respimat® SMI (see [Appendix 4](#)).

20.2.1 Analysis of Secondary Outcomes

20.2.1.1 Domain PASAPQ Scores and Overall Satisfaction Score

Analysis Set: FAS

One of the secondary objectives of the study is to examine the performance domain score of the PASAPQ, the convenience domain score of the PASAPQ, and the overall satisfaction score of the PASAPQ at study end.

The secondary analysis of these outcomes will be performed overall and by patient cohort. All data required for this analysis will be collected from the “PASAPQ (ePRO)” or “PASAPQ (Paper)” eCRF pages. The first 13 items will generate the performance domain (7 items: Q1-5

Document: \\ .net\Enterprise\Sites\USCBG\Depts\BioStat\Boehringer\Documentation\SAP\Final
Author: Version Number: 1.0
Version Date: 100CT2019

Template No.: RWI_TP_BIOS0013 Revision 1

Reference: RWI_WI BIOS0015

Effective Date: 15Jun2018

and Q10-11) and the convenience domain (6 items: Q6-9 and Q12-13). Question 14 will ask for the overall satisfaction with the device used in the study.

Performance PASAPQ score and convenience PASAPQ score will be summarised using descriptive statistics for continuous variables, while the overall satisfaction score will be summarised using descriptive statistics for categorical variables.

Derivations:

For performance and convenience PASAPQ domain scores, derivations will be handled in the same way as for the primary analysis, which are described in [Section 20.1.1](#). No scoring derivation will be performed for overall satisfaction score.

20.2.1.2 Re-usable Respimat® SMI Willingness

Analysis Set: FAS

The secondary analysis to evaluate the willingness to continue with the re-usable Respimat® SMI used in the study will be performed overall and by patient cohort. It will be evaluated through Question 15 of the PASAPQ collected under the “PASAPQ (ePRO)” or “PASAPQ (Paper)” eCRF pages. This score ranges from 0 to 100, with 0 indicating that the patient would not be willing to continue using this inhaler and 100 indicating that the patient would definitely be willing to continue using this inhaler

Willingness to continue with the re-usable Respimat® SMI Inhaler will be summarised using descriptive statistics for continuous variables.

Document: \\ .net\Enterprise\Sites\USCBG\Depts\BioStat\Boehringer\Documentation\SAP\Final

Author: Version Number: 1.0

Version Date: 100CT2019

Template No.: RWI_TP_BIOS0013 Revision 1

Reference: RWI_WI_BIOS0015

Effective Date: 15Jun2018

20.2.1.3 Re-usable Respimat® SMI Ease of Handling

Analysis Set: FAS

The secondary analysis to evaluate the ease of handling of re-usable Respimat® SMI used in the study will be performed overall and by patient cohort.

Ease of handling will be accessed using a set of individual items with answers ranging from 1 (very dissatisfied) to 7 (very satisfied) and will be collected from the “Ease of Handling (ePRO)” or “Ease of Handling (Paper)” eCRF pages.

The following ease of handling of re-usable Respimat® SMI items will be summarised using descriptive statistics for categorical variables:

- Q1: How satisfied are you with the ease of removing the clear base?
- Q2: How satisfied are you with the grip of the cartridge?
- Q3: How satisfied are you with inserting a new cartridge?
- Q4: How satisfied are you with the readability of the dose indicator?
- Q5: How satisfied are you with recognising when you need to replace the cartridge?
- Q6: How satisfied are you with automatic detachment of the clear base when the cartridge is empty?
- Q7: How satisfied are you with automatic return to the start-use position when replacing the clear base?
- Q8: How satisfied are you with the overall ease of handling the inhaler?
- Q9: How satisfied are you with the sustainability (eco-friendly) concept of the inhaler, due to re-use ability?

Document: \\ .net\Enterprise\Sites\USCBG\Depts\BioStat\Boehringer\Documentation\SAP\Final

Author: Version Number: 1.0
Version Date: 100CT2019

Template No.: RWI_TP_BIOS0013 Revision 1

Reference: RWI_WI_BIOS0015

Effective Date: 15Jun2018

- Q10: How satisfied are you with recognising when to replace the inhaler?

20.2.1.4 Total PASAPQ Score

Analysis Set: FAS

The total PASAPQ score at study entry (baseline visit) and study end (follow-up assessment) will be summarised using descriptive statistics for continuous variables for the subgroup of Respimat® SMI-experienced patients switching from a disposable to a re-usable Respimat® SMI at study entry.

The absolute change from baseline in total PASAPQ score will also be summarised at study end and will be examined using a two-tailed t-test for paired samples or an appropriate non-parametric test (e.g. Wilcoxon signed ranks test), depending on the distributions of the count/score data. The 95% CI for the difference of the means of the total PASAPQ score will also be presented.

Same analysis will be performed for performance and convenience PASAPQ scores.

Derivations:

- *Absolute change of total PASAPQ score = (Total PASAPQ score at follow-up assessment – Total PASAPQ score at baseline visit).*
- *Absolute change of performance score = (Performance score at follow-up assessment – Performance score at baseline visit).*

Document:	\	.net\Enterprise\Sites\USCBG\Depts\BioStat\Boehringer\Documentation\SAP\Final
Author:		Version Number: 1.0

Template No.: RWI_TP_BIOS0013 Revision 1

Reference: RWI_WI_BIOS0015

Effective Date: 15Jun2018

- *Absolute change of convenience score = (Convenience score at follow-up assessment – Convenience score at baseline visit).*

20.2.1.5 *Respimat® SMI Preference*

Analysis Set: FAS

The secondary analysis to determine the preference for re-usable or disposable Respimat® SMI will be performed for Respimat® SMI-experienced patients switching from a disposable to a re-usable Respimat® SMI at study entry.

The preference for the disposable or re-usable Respimat® SMI will be collected by a single question collected in the “Patient Preference (ePRO)” or “Patient Preference (Paper)” eCRF pages. The following will be summarised using descriptive statistics for categorical variables:

- Q1: Comparing the re-usable with disposable inhaler, please indicate which inhaler do you prefer to use?: Re-usable inhaler, Disposable inhaler, No preference.

20.2.2 Missing Data Methods for Secondary Outcomes

For performance and convenience PASAPQ domain scores, missing data will be handled in the same way as for the primary analysis, which are described in [Section 20.1.2](#).

21. SAFETY OUTCOMES

21.1 Adverse Events

Analysis Set: FAS

Document:	\	.net\Enterprise\Sites\USCBG\Depts\BioStat\Boehringer\Documentation\SAP\Final	
Author:		Version Number:	1.0

Template No.: RWI_TP_BIOS0013 Revision 1

Reference: RWI_WI_BIOS0015

Effective Date: 15Jun2018

Adverse Events (AEs) reported during the study period will be coded using the latest version of MedDRA at the time of DBL and will be analysed overall and by patient cohort using the information collected under the “Adverse Event”/ “Adverse Event Details” eCRF pages.

21.1.1 All Adverse Events

An overall summary of AEs table will include the following:

- Number (%) of patients having at least one AE.
- Number (%) of patients having at least one non-serious AE (Non-SAE).
- Number (%) of patients having at least one serious adverse event (SAE).
- Number (%) of patients having at least one fatal SAE.
- Number (%) of patients having at least one non-fatal SAE.
- Number (%) of patients having at least one AE requiring treatment discontinuation.
- Number (%) of patients having at least one adverse drug reaction (ADR).
- Number (%) of patients having at least one non-serious ADR.
- Number (%) of patients having at least one serious ADR.
- Number (%) of patients having at least one ADR requiring treatment discontinuation.
- Number (%) of patients having at least one other reportable safety event associated with an AE.

In addition, all the AEs reported during the study period will be summarised as the number and percentage of patients experiencing an AE by MedDRA primary SOC as body system category and PT as an event category. If a patient has more than one occurrence of the same AE, the patient will be counted only once within each PT or SOC. Adverse events will be displayed in

Document:	\	.net\Enterprise\Sites\USCBG\Depts\BioStat\Boehringer\Documentation\SAP\Final	
Author:		Version Number:	1.0

Template No.: RWI_TP_BIOS0013 Revision 1

Reference: RWI_WI_BIOS0015

Effective Date: 15Jun2018

terms of frequency tables sorted on alphabetical order of SOC and decreasing frequency of PT within a given SOC. In case of equal frequency regarding PT, alphabetical order will be used. The number of AEs will also be presented. In case any AE does not have MedDRA SOC coded term, it will be summarised under the “Unavailable MedDRA SOC classification” category.

Similar tables will be created as stated above for: non-SAEs, SAEs, fatal SAEs, non-fatal SAEs, AEs requiring treatment discontinuation, ADRs, non-serious ADRs, serious ADRs and ADRs requiring treatment discontinuation.

Supportive listings will be provided.

21.1.2 Adverse Drug Reactions

An ADR is defined as a response to a medicinal product which is noxious and unintended. Response in this context means that a causal relationship between a medicinal product and an AE is at least a reasonable possibility.

Adverse drug reactions are those events recorded as “Relationship to Study Treatment = Yes” on the “Adverse Events Details” eCRF page.

21.1.3 Serious Adverse Events

An SAE is any untoward medical occurrence which:

- Results in death.
- Is life-threatening.
- Requires inpatient hospitalisation or prolongation of existing hospitalisation.

Document: \\ .net\Enterprise\Sites\USCBG\Depts\BioStat\Boehringer\Documentation\SAP\Final

Author: Version Number: 1.0

Version Date: 100CT2019

Template No.: RWI_TP_BIOS0013 Revision 1

Reference: RWI_WI_BIOS0015

Effective Date: 15Jun2018

- Results in persistent or significant disability or incapacity.
- Is a congenital anomaly or birth defect.

SAEs are those events recorded as “Serious = Yes” on the “Adverse Events Details” eCRF page.

21.1.4 Fatal Serious Adverse Events

Fatal SAEs are those events recorded as “Outcome = Fatal” on the “Adverse Events Details” eCRF page. Otherwise, SAEs will be classified as non-fatal SAEs.

21.1.5 Non-Serious Adverse Events

Non-SAEs are those events recorded as “Serious = No” on the “Adverse Events Details” eCRF page.

21.1.6 Adverse Events Requiring Treatment Discontinuation

Adverse events requiring treatment discontinuation are those events recorded as “Action Taken with Study Treatment = Drug Withdrawn” on the “Adverse Events Details” eCRF page.

21.1.7 Other Reportable Safety Events

Analysis Set: FAS

Other Reportable Safety Events during the study period will be collected if they occur in conjunction with an AE, such as:

- Overdose/under dose.

Document: \\ .net\Enterprise\Sites\USCBG\Depts\BioStat\Boehringer\Documentation\SAP\Final

Author: Version Number:

1.0

Version Date:

100CT2019

Template No.: RWI_TP_BIOS0013 Revision 1

Reference: RWI_WI BIOS0015

Effective Date: 15Jun2018

- Drug interaction.
- Exposure.
- Medication error.
- Product confusion.
- Use of product outside of product label/authorised product information.
- Lack (or loss) of effect.
- Unexpected therapeutic benefit/effect.

Other Reportable Safety Events associated with an AE will be documented in the “Adverse Event Details” eCRF page as additional information regarding an AE and will be analysed overall and by patient cohort.

Document:	\\ .net\Enterprise\Sites\USCBG\Depts\BioStat\Boehringer\Documentation\SAP\Final
Author:	Version Number: 1.0 Version Date: 100CT2019

Template No.: RWI_TP_BIOS0013 Revision 1

Reference: RWI_WI_BIOS0015

Effective Date: 15Jun2018

23. APPENDICES

23.1 APPENDIX 1. Conversion Factors

The following conversion factors will be used:

- Height:

1 in = 2.54 cm.

- Weight:

1 lb = 0.4536 kg.

- Dates:

1 week = 7 days.

1 month = 30.4375 days.

1 year = 365.25 days.

1 year = 52.18 weeks.

1 year = 12 months.

- Smoking:

20 cigarettes = 1 pack.

Document: \\ .net\Enterprise\Sites\USCBG\Depts\BioStat\Boehringer\Documentation\SAP\Final

Author: Version Number: 1.0

Version Date: 100CT2019

Template No.: RWI_TP_BIOS0013 Revision 1

Reference: RWI_WI_BIOS0015

Effective Date: 15Jun2018

23.2 APPENDIX 2. Partial Date Conventions

Partial dates will be imputed as follows:

Previous and Concomitant Medications:

Incomplete dates for previous/concomitant medications will be imputed as follows:

- If the medication start date is missing completely, then the medication date will be replaced by the signed ICF date.
- If the day of medication start date is missing, but the month and year are equal to the signed ICF date, then the medication date will be replaced by the signed ICF date.
- If both the day and month of the medication start date are missing but the year is equal to the signed ICF year, then the medication start date will be replaced by the signed ICF date.
- In all other cases, the missing medication day or missing medication month will be replaced by 1.
- Incomplete medication stop date will be replaced by the last day of the month (if day is missing only), if not resulting in a date later than the date of the subject's death. In the latter case, the date of death will be used to impute the incomplete stop date.
- In all other cases, the incomplete medication stop date will not be imputed.

Disease History and Spirometry:

Incomplete dates for date of COPD diagnosis and date of last available spirometry assessment prior to study entry will be imputed as follows:

Document:	\	.net\Enterprise\Sites\USCBG\Depts\BioStat\Boehringer\Documentation\SAP\Final	
Author:		Version Number:	1.0

Template No.: RWI_TP_BIOS0013 Revision 1

Reference: RWI_WI_BIOS0015

Effective Date: 15Jun2018

- If the day is missing, it will be imputed to the 15th day of the month.
- If both day and month are missing and the year is prior to the year of the signed ICF date, the month and day will be imputed as July 1st.
- If both day and month are missing and the year is the same as the year of the signed ICF date, the month and day will be imputed as January 1st.
- If the date is completely missing, no imputation will be performed.

Exposure:

Incomplete and partial dates for date of first use of re-usable Respimat® SMI prior to study entry will be imputed as follows:

- If the day is missing, it will be imputed to the 15th day of the month.
- If both day and month are missing and the year is prior to the year of the signed ICF date, the month and day will be imputed as July 1st.
- If both day and month are missing and the year is the same as the year of the signed ICF date, the month and day will be imputed as January 1st.
- If the date is completely missing, no imputation will be performed.

Incomplete and partial dates for date of first use and date of last use of disposable Respimat® SMI prior to study entry will be imputed as follows:

- If the day of first use of disposable Respimat® SMI date is missing, it will be imputed to the 15th day of the month.

Document: \\ .net\Enterprise\Sites\USCBG\Depts\BioStat\Boehringer\Documentation\SAP\Final

Author: Version Number: 1.0

Version Date: 100CT2019

Template No.: RWI_TP_BIOS0013 Revision 1

Reference: RWI_WI_BIOS0015

Effective Date: 15Jun2018

- If both day and month of first use of disposable Respimat® SMI date are missing but the first use year is prior to the year of the signed ICF date, the month and day will be imputed as July 1st.
- If both day and month of first use of disposable Respimat® SMI date are missing but the first use year is equal to the year of the signed ICF date, the month and day will be imputed as January 1st.
- If the disposable Respimat® SMI first use date is completely missing, no imputation will be performed.
- Incomplete disposable Respimat® SMI last use date will be replaced by the last day of the month (if day is missing only).
- If the disposable Respimat® SMI last use date is completely missing, it will be imputed by the signed ICF date.

Incomplete and partial dates for prescribed date of re-usable Respimat® SMI at study entry will be imputed as follows:

- If the day of prescribed date of re-usable Respimat® SMI at study entry is missing, but the month and year are equal to the dispensed date, then the prescribed date will be replaced by the dispensed date.
- If both day and month of prescribed date of re-usable Respimat® SMI at study entry are missing but the prescribed year is equal to the year of the dispensed date, then the prescribed date will be replaced by the dispensed date.
- In all other cases, the missing day of the prescribed date of re-usable Respimat® SMI at study entry will be replaced by 1.

Document: \\ .net\Enterprise\Sites\USCBG\Depts\BioStat\Boehringer\Documentation\SAP\Final

Author: Version Number: 1.0

Version Date: 100CT2019

Template No.: RWI_TP_BIOS0013 Revision 1

Reference: RWI_WI_BIOS0015

Effective Date: 15Jun2018

- If the prescribed date is missing, it will be imputed by the dispensed date. If the dispensed date is missing, prescribed date will be imputed by the signed ICF date.

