4. STUDY DESIGN

4.1 General Description

This is a multicentre, open-label, prospective, real-world non-interventional study of patients with COPD, prescribed with re-usable Respimat® SMI. Patient enrolment will commence in September 2019 and is expected to end in December 2019. The last patient last assessment is expected in February 2020 (see Section 6 of the Clinical Study Protocol [CSP] for details of study milestones).

For this study, two patient cohorts will be defined according to the prescription of a Respimat® SMI product:

- 1) Respimat® SMI-experienced, defined as patients who have been on maintenance treatment with a Respimat® SMI product (Spiriva®, Striverdi® or Spiolto®) and receive a refill prescription at study entry. This patient cohort will further be divided into two subgroups:
 - 1a) Patients on maintenance treatment with a re-usable Respimat® SMI at study entry.
 - 1b) Patients on maintenance treatment with a disposable Respimat® SMI and switching to a re-usable Respimat® SMI at study entry.
- 2) Respimat® SMI-naïve, defined as patients who have not previously used a Respimat® SMI product and receive their first prescription at study entry.

The prescription at study entry for both patient cohorts should be for a re-usable Respimat® SMI product.

Document:	\	.net\Enterprise\Sites\USCBG\Depts\BioStat\Boehringer\Documentation\SAP\Final
Author:		Version Number: 1.0

Template No.: RWI_TP_BIOS0013 Revision 1

Reference: RWI_WI_BIOS0015

Effective Date: 15Jun2018

The study population will be identified by the participating physicians involved in the diagnosis, treatment and management of COPD patients (general practitioners and/or specialist physicians including pneumologists). Eligible patients must be prescribed and use a re-usable Respimat® SMI product (as per the routine clinical practice of the participant sites) after being prescribed a Respimat® SMI product for the first time in the course of standard clinical practice (Respimat® SMI-naïve patients) or after having switched from a disposable Respimat® SMI (Respimat® SMI-experienced patients).

[figure not shown]

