8.4 Baseline Visit

The routine visit, at which a patient is enrolled in the study (time of ICF signature), will be treated as the baseline (study entry) visit.

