12.5 Spirometry

Last pre-bronchodilator and post-bronchodilator spirometry measurements available in the 12-month period prior to study entry will be summarised with descriptive statistics using the information collected from the “Post-Bronchodilator Spirometry Measurement” eCRF page. Spirometry data will include:

- Time since last available spirometry assessment (months) - calculated relative to signed ICF date.
- Forced vital capacity (FVC) (L).
- Forced expiratory volume (FEV₁) (L).
- FEV₁/FVC ratio (%).
 - FEV₁/FVC ratio (%) categories: <70%, ≥70%.
- FVC predicted (L) – calculated based on European Coal and Steel Community (ECSC) equations [\[4\]](#).
- FEV₁ predicted (L) – calculated based on ECSC equations [\[4\]](#).
- FVC predicted (%).
- FEV₁ predicted (%).

Derivations:

- *Time since last available spirometry assessment (months) = [(date of signed ICF – date of last available spirometry assessment) + 1] / 30.4375.*
- *FVC predicted (L):*

Document:	\	.net\Enterprise\Sites\USCBG\Depts\BioStat\Boehringer\Documentation\SAP\Final
Author:		Version Number: 1.0

Template No.: RWI_TP_BIOS0013 Revision 1

Reference: RWI_WI_BIOS0015

Effective Date: 15Jun2018

- *Males: $FVC_{predicted}(L) = 0.0576 * (Height [cm]) - 0.026 * Age (years) - 4.34$, where $Age (years) = (year of last available spirometry assessment - year of birth)$ and $Height (cm) = Height (cm)$ collected from the “Vital Signs” eCRF page.*
- *Females: $FVC_{predicted}(L) = 0.0443 * (Height [cm]) - 0.026 * Age (years) - 2.89$, where $Age (years) = (year of last available spirometry assessment - year of birth)$ and $Height (cm) = Height (cm)$ collected from the “Vital Signs” eCRF page.*
- $FEV_1_{predicted}(L)$:
 - *Males: $FEV_1_{predicted}(L) = 0.043 * (Height [cm]) - 0.029 * Age (years) - 2.49$, where $Age (years) = (year of last available spirometry assessment - year of birth)$ and $Height (cm) = Height (cm)$ collected from the “Vital Signs” eCRF page.*
 - *Females: $FEV_1_{predicted}(L) = 0.0395 * (Height [cm]) - 0.025 * Age (years) - 2.60$, where $Age (years) = (year of last available spirometry assessment - year of birth)$ and $Height (cm) = Height (cm)$ collected from the “Vital Signs” eCRF page.*
- $FVC_{predicted} (\%) = [FVC(L) / FVC_{predicted}(L)] * 100$.
- $FEV_1_{predicted} (\%) = [FEV_1(L) / FEV_1_{predicted}(L)] * 100$.

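### The SAP's 1 July rule puts a spirometry date known only as 2018 outside the 12-month window for every planned enrolment date, so the reported time since spirometry comes out at 13 to 18 months

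*SAP*

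**What the plan says.** SAP section 12.5 restricts the lung-function summary to the last "spirometry measurements available in the 12-month period prior to study entry". Footnote 1 to Table 1, in both the protocol and the SAP, uses the same period. Section 8.4 fixes study entry as the visit "at which a patient is enrolled in the study (time of ICF signature), will be treated as the baseline (study entry) visit", so the window runs back 12 months from the consent (ICF) date.

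Section 12.5 also derives "Time since last available spirometry assessment (months) - calculated relative to signed ICF date", using days between the two dates plus one, divided by 30.4375.

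Appendix 2, under Disease History and Spirometry, gives one list of rules for the COPD diagnosis date and the "date of last available spirometry assessment prior to study entry will be imputed as follows". The rule at issue applies when day and month are both missing: if "the year is prior to the year of the signed ICF date, the month and day will be imputed as July 1st". A year-only date in the consent year becomes 1 January. Neither rule refers to the 12-month window.

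On timing, SAP section 4.1 says "Patient enrolment will commence in September 2019 and is expected to end in December 2019". Protocol section 9.2.1 has enrolment starting in August 2019 and ending in the same month as the SAP.

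**The concern.** Mid-year imputation is a reasonable neutral choice for a diagnosis date, which may lie many years back. It does not suit a date already known to fall within one year of consent. With consent in the last five months of 2019, an eligible 2018 test can only have been done late in 2018, between the consent date less 12 months and 31 December. The rule places it before that interval.

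The report would then show times since spirometry above 12 months in a table restricted to the previous 12 months. The SAP is also silent on whether the window is checked on the recorded or the imputed date, which leaves the programmer to decide whether the record is kept.

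**Working it through.** The documents give no calculated figure on this point, so there is nothing to reproduce first.

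**Inputs**
- Imputed date for a year-only 2018 test: 1 July 2018 (SAP Appendix 2).
- Window: consent date less 12 months, up to the consent date (SAP sections 12.5 and 8.4).
- Consent dates: 1 August (protocol 9.2.1) or 1 September (SAP 4.1) to 31 December 2019.
- Formula: months = (consent date − spirometry date + 1) / 30.4375 (SAP section 12.5, Appendix 1).

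**Step 1: is 1 July 2018 ever in the window?** It is inside only if the consent date less 12 months is 1 July 2018 or earlier, that is, for consent on or before 1 July 2019. Planned enrolment starts later. Of the 153 dates from 1 August to 31 December 2019, none qualifies.

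**Step 2: what does the formula return?** The true range is for a 2018 test that really is in the window, from one done on 31 December 2018 to one done exactly 12 months before consent (366 / 30.4375 = 12.02).

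| Consent date (2019) | Days from 1 Jul 2018, plus 1 | Months by SAP formula | True range, months | Overstatement, months |
|---|---|---|---|---|
| 1 Aug | 397 | 13.04 | 7.03 to 12.02 | 1.0 to 6.0 |
| 1 Sep | 428 | 14.06 | 8.05 to 12.02 | 2.0 to 6.0 |
| 15 Oct | 472 | 15.51 | 9.50 to 12.02 | 3.5 to 6.0 |
| 1 Dec | 519 | 17.05 | 11.04 to 12.02 | 5.0 to 6.0 |
| 31 Dec | 549 | 18.04 | 12.02 | 6.0 |

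For 15 October, 472 / 30.4375 = 15.51, and a test on 31 December 2018 gives 289 / 30.4375 = 9.50.

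**Step 3: is the same-year rule affected?** No. A year-only 2019 date becomes 1 January 2019, giving 213 / 30.4375 = 7.00 months for consent on 1 August and 365 / 30.4375 = 11.99 for 31 December. Both are inside the window, so only the prior-year branch fails.

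**Step 4: how many days of 2018 are in the window?** For consent on 1 August 2019, 153 of 365 days (42%). For 1 September, 122 (33%). For 1 December, 31 (8%). For 31 December, 1. A year-only 2018 date therefore does not itself show that the test was eligible.

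**Step 5: what else uses the imputed month and day?** Predicted FEV1 and FVC in section 12.5 use age computed from calendar years, so month and day do not enter. FEV1, FVC and their ratio are measured. GOLD grade and group come from a separate eCRF page (section 12.4). The PASAPQ analyses do not use the spirometry date.

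**The case against.** A reader might infer that valid lung-function results are lost, or that the table describing airflow limitation is wrong whichever way the SAP is read. The documents do not support either. No section describes a filter comparing an imputed date with the window. Section 12.5 can be read as a restriction already applied when the data are collected. If the record stays, no airflow value changes.

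There are also safeguards. SAP section 9.3 flags variables derived from imputed values in the listings, section 5.2 plans a dry run and a data review meeting, and protocol section 9.6 provides edit checks for out-of-range or illogical data. An age of 15 months may well be noticed. These steps make the error easier to see, but none changes the rule.

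Two further objections stand. Some year-only 2018 tests may really be older than 12 months, and for those a value above 12 may be nearer the truth. In addition, imputing inside the window makes every such test look eligible and removes the signal that would prompt a query. The fix therefore includes a site query.

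Finally, 12 months is implied by the window and is not stated as a limit on the derived variable. By the SAP's formula, a test exactly 12 months old already gives 12.02. That rounding does not explain values of 13 to 18.

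**Conclusion.** The point holds as a small inconsistency within the SAP. For a spirometry date known only as 2018, the stated rule cannot give a date inside the SAP's own window, and the derived time is 13.0 to 18.0 months. For a test truly in the window, that overstates its age by between 1 and 6 months.

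The effect is confined to one descriptive baseline row, unless the window is applied to imputed dates. In that case the patient's FEV1 and FVC would also leave the spirometry table. The SAP leaves this open, so it is a possibility to close off and not a consequence of the plan as written.

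The conclusion assumes consent dates within the planned 2019 enrolment period. The size in patients cannot be stated: spirometry is collected only if available, and the documents do not give the share of year-only dates. It may be small or zero.

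**What to change.** In SAP Appendix 2, separate the two variables and keep 1 July for the COPD diagnosis date. For spirometry with only the year known and equal to the consent year minus one, bound the imputed date to the window, for example at the midpoint between the consent date less 12 months and 31 December of that year. For consent on 15 October 2019, the interval is 15 October to 31 December 2018 (77 days). The midpoint, rounded down to 38 days, is 22 November 2018, which gives 328 / 30.4375 = 10.8 months.

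In section 12.5, state that the 12-month restriction is applied to eligibility as recorded on the eCRF and not to the imputed date. Query year-only spirometry dates with the site, so that a test outside the window is not made to look eligible by the imputation.

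The cost is a few sentences in the SAP, about one line of programming, and one routine query per affected record, all before database lock.
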